9. STATISTICAL CONSIDERATIONS

9.1. Statistical Hypothesis and Sample Size Determination

The study will utilize the Simon two-stage optimal design (Figure 1 and Table 8) and will include up to 67 to 73 subjects, depending on IP dose evaluated in Stage 1 and Stage 2 as follows:

- if the AL101 dose is 6 mg QW throughout the study, there will be up to 67 subjects evaluated, including the 6 subjects in the lead-in cohort for the Stage 1 evaluation.
- if AL101 4 mg is evaluated in Stage 1 and Stage 2, there will be up to 73 enrolled subjects consisting of up to 67 subjects at AL101 4 mg and 6 subjects in the lead-in cohort of AL101 6 mg. Note, the lead-in cohort will not be included in the Stage 1 evaluation.

In both scenarios there will be up to 26 evaluable subjects in Stage 1, and 41 additional evaluable subjects in Stage 2 provided at least 4 subjects (out of 26) responded in Stage 1.

While the data on Stage 1 is maturing, Stage 2 will continue enrolling an additional 41 subjects, unless an unexpected safety signal emerges that in the judgement of the DMC requires analysis and/or poses a serious threat to the well-being of the subject. This decision will be made in agreement with the Sponsor.

If no more than 3 subjects respond in Stage 1, the study will be stopped for futility. If 4 or more subjects respond, Stage 1 will be considered positive. For the entire study (Stages 1 and 2), the null hypothesis will be rejected if 15 or more responses are observed in 67 subjects. Only the Efficacy Evaluable set of subjects will be counted toward this analysis. This design has 80% power at the 5% type I error level to detect a desirable success rate of 23% against the null hypothesis of an unacceptable success rate of 11%. The success rate parameters for the two-stage design are aligned with recent published experience of clinical studies (Twelves, 2014). If at the end of Stage 1, there are 4 responses in the Notch-activated TNBC subjects, the study will continue to Stage 2.

Table 8 Sample Size Hypothesis

Total	Look1	Futility Boundary		Attained	Attained	Probability of	Expected
							Sample Size
(n)	(n_1)	Look1	Look2	Alpha	Power	Early	H0 (EN0)
		(r_1)	(r_2)			Stopping	
67	26	3	11	0.049	0.807	0.681	39.1

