9.2. Analysis Populations

The following analysis sets will be used in this study:

- Safety analysis population: All subjects who receive at least one dose of IP (even a partial dose).

- Efficacy evaluable population: All subjects who receive at least one dose of IP at the dose as determined by the lead-in cohort, have measurable disease at baseline per RECIST v1.1, and have at least one post-baseline on-study assessment of tumor response, unless there is documented clinical progression after discussion with Sponsor's Medical Monitor or radiological progression prior to Week 8.
- Per-protocol (PP) analysis population: All efficacy evaluable subjects who have no major protocol violations, as defined by the Sponsor prior to database lock.

Note: if there is a discrepancy between the Notch-activated mutation determination between commercial/LDT NGS assay and the confirmatory central assay, the subject will be non-evaluable for the Efficacy and PP evaluations.

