9.3. Statistical Analyses

The statistical analysis plan (SAP) will be finalized prior to database lock and it will include a more technical and detailed description of the statistical analyses described in this section. This section is a summary of the planned statistical analyses of the most important endpoints including primary and key secondary endpoints.

The standard summary statistics for continuous variables are sample size (n), mean, standard deviation, median, minimum and maximum. The standard summary statistics for categorical variables are frequencies and percentages. Time to event variables will be summarized using the Kaplan-Meier method. Where confidence limits are appropriate, the confidence level will be 95% (two-sided), unless otherwise stated. The only test of statistical significance will be performed according to the pre-defined analysis of the Simon two-stage optimal design.

Individual data (including relevant derived variables) will be presented by parameter in listings. Results of statistical analyses, descriptive summary statistics and supportive listings will also be presented.

Baseline values are defined as the last valid value prior to IP administration. Baseline safety data will be presented along with subsequent safety values assessed during or after drug administration.

Detailed methodology for summary and statistical analyses of the data collected in this study will be documented in a statistical analysis plan (SAP), which will be maintained by the Sponsor. This document may modify the plans outlined in the protocol; however, any major modifications will also be reflected in a protocol amendment.

Statistical analyses will be performed using SAS® v9.4 or higher (SAS Institute, Cary NC, USA).

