9.4. Interim Analyses

Because a Simon two-stage optimal design will be employed, ORR will be assessed during Stage 1 for subjects who have received IP for at least 2 cycles (8 weeks) and no more than 8 cycles (8 months). While the data on Stage 1 is maturing, Stage 2 will continue enrolling an additional 41 subjects for a total of 67 subjects, unless an unexpected safety signal emerges that in the judgement of the DMC requires analysis and/or poses a serious threat to the well-being of the subject.

The Statistical Analysis Plan will describe the planned analyses in greater detail.

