9.5. Data Monitoring Committee (DMC)

An independent Data Monitoring Committee (DMC) will be assigned by the Sponsor prior to the beginning of the study. Throughout the study, the DMC will monitor safety parameters at regular intervals (approximately quarterly) after at least 3 subjects have been treated for at least 2 cycles (after the first on-treatment radiographic assessment) and then periodically as specified in the DMC charter. Efficacy data will also be provided to the DMC to allow assessment of benefit/risk for subjects. The DMC may recommend stopping the study if at any time during the study there are unacceptable AEs or safety concerns as described in the protocol stopping rules defined in the DMC charter.

For each DMC meeting, pre-specified reports will be provided. In addition, the DMC Chair will be provided with or have access to periodical safety and efficacy reports as specified in the DMC charter. The DMC Chair may share these reports with the DMC or convene additional meetings of the DMC at his/her discretion. The DMC Chair may request additional safety and efficacy data based on the review of study data.

Further details regarding data safety monitoring guidelines will be included in the DMC Charter, which is the governing document that supersedes this section of the protocol.

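### The only SAP deadline is database lock, so details that decide the Stage 1 response count can be settled after the open-label responses are known

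*Combined protocol and SAP*

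**What the plan says.** **Timing of the SAP.** Section 9.3 sets one deadline: "The statistical analysis plan (SAP) will be finalized prior to database lock". The same section lets the SAP depart from the protocol: "This document may modify the plans outlined in the protocol; however, any major modifications will also be reflected in a protocol amendment". Section 9.4 says of the interim analysis: "The Statistical Analysis Plan will describe the planned analyses in greater detail". No section ties the SAP to the Stage 1 look or describes an interim SAP or interim lock. Section 10.1.5 places the end of the study after the last subject's 30-day visit.

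**What is already fixed.** Section 9.1 gives the Stage 1 rule, "If no more than 3 subjects respond in Stage 1, the study will be stopped for futility", with 26 subjects in Stage 1, and says that only the Efficacy Evaluable set counts. Section 9.2 defines that set. Section 9.3.3.1 requires RECIST v1.1 responses confirmed no earlier than 4 weeks later.

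**What is loosely fixed.** Section 9.4 says that response rate is "assessed during Stage 1 for subjects who have received IP for at least 2 cycles (8 weeks) and no more than 8 cycles". Sections 9.1 and 9.4 let Stage 2 enrol while Stage 1 matures. Section 9.2 makes a subject non-evaluable if the central Notch assay disagrees with the local one, while Section 8.4.1 makes central confirmation optional. For the final test Section 9.1 says "the null hypothesis will be rejected if 15 or more responses are observed in 67 subjects", but Table 8 lists a second-look futility bound of 11.

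**The concern.** A go/no-go that turns on a single response needs its counting rules fixed before anyone knows who has responded. In a masked trial, finalising the SAP before database lock gives that protection. Here there is one arm, no masking and investigator-read response, so lock conceals nothing. Lock also comes too late for Stage 1: that decision determines whether the study runs to 67 subjects, and no earlier lock is described. A sponsor that follows Section 9.3 to the letter can take the futility look before the document meant to detail it exists. At stake are the chance of continuing with an inactive drug and, to a lesser degree, the type I error.

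**Working it through.** **1. Reproduce Table 8.** Inputs from Section 9.1 and Table 8: n1 = 26, stop at 3 or fewer, n = 67 (so 41 in Stage 2), null rate 0.11, alternative 0.23. X1 ~ Bin(26, p), X2 ~ Bin(41, p), and c is the final cut-off.

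- Early stopping = P(X1 ≤ 3) = 0.6807 at p = 0.11.
- Expected size = 26 + (1 − 0.6807) × 41 = 39.09.
- P(reject) = sum over x ≥ 4 of P(X1 = x) × P(X2 ≥ c − x).

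| Final cut | Type I error | Power |
|---|---|---|
| 12 or more (Table 8, r2 = 11) | 0.0494 | 0.807 |
| 15 or more (text of Section 9.1) | 0.0051 | 0.573 |

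Table 8 prints 0.049, 0.807, 0.681 and 39.1. It is reproduced with a cut of 12 and not with a cut of 15.

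**2. What the protocol leaves open.**

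- *Data cut.* Anything from 2 to 8 cycles, with no date or trigger.
- *Subjects with only 2 cycles.* First scan at 8 weeks plus at least 4 weeks to confirmation is at least about 12 weeks. Such a subject can enter the Section 9.4 assessment but cannot yet have the confirmed response that Section 9.3.3.1 requires. No rule says how that subject counts.
- *Which 26.* With Stage 2 enrolling, more than 26 subjects may be on study at the look, and no rule assigns Stage 1 membership.
- *Evaluability.* Clinical progression before Week 8 counts after discussion with the Medical Monitor, and optional central Notch testing can remove subjects.
- *Final cut-off.* 15 in the text, 12 from Table 8.

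**3. Size at Stage 1.** At p = 0.11, P(X1 ≥ 4) = 0.3193 and P(X1 = 3) = 0.2372. Let q be the chance that a late choice turns 3 counted responses into 4. The documents give no value for q, so a range is shown; q = 0.11 corresponds to replacing one subject by another whose outcome is not yet known.

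- P(continue) = 0.3193 + q × 0.2372.
- Added type I error = q × 0.2372 × P(X2 ≥ c − 3). For c = 12, P(X2 ≥ 9) = 0.0316, so it is q × 0.00749. For c = 15, P(X2 ≥ 12) = 0.00115, so it is q × 0.00027.

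| q (assumed) | P(continue) | Type I error, cut 12 | Type I error, cut 15 |
|---|---|---|---|
| 0 | 0.319 | 0.0494 | 0.0051 |
| 0.11 | 0.345 | 0.0502 | 0.0052 |
| 0.50 | 0.438 | 0.0532 | 0.0053 |
| 1 | 0.556 | 0.0569 | 0.0054 |

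These rows assume that the extra Stage 1 response opens Stage 2 but is not kept in the final total. If it is kept, Stage 2 needs one response fewer. At q = 1 and a cut of 12, P(X2 ≥ 8) = 0.0753 and type I error is 0.0494 + 0.2372 × 0.0753 = 0.0673. At a cut of 15, P(X2 ≥ 11) = 0.0039 and it is 0.0051 + 0.2372 × 0.0039 = 0.0060.

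**4. Size of the membership question.** If the counted set grows while the boundary stays at 4, P(4 or more) at p = 0.11 is 0.319 with 26 subjects, 0.372 with 28 and 0.423 with 30.

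**5. Size of the cut-off question.** The two final rules disagree when the study passes Stage 1 and ends with 12 to 14 responses. That probability is 0.0494 − 0.0051 = 0.044 at a true rate of 11%, and 0.807 − 0.573 = 0.234 at 23%.

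**The case against.** The core of the response analysis does not wait for the SAP. The Stage 1 boundary, analysis set, response criteria and confirmation rule are in the protocol, and Section 9.3 describes the SAP as a more technical elaboration. Major modifications need a protocol amendment, and Section 10.1.3.1 adds ethics approval before changes that affect scientific quality take effect. The text reviewed contains no separate SAP, so its actual date is unknown; it may have been signed early. Removing a subject as non-evaluable does not create a responder, so q = 1 is an extreme.

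Most of this stands, and it limits the point to the open items listed above. It does not close the gap. Neither section sets a date relative to the response data, *major* is not defined, and filling a silence may not count as a modification at all.

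Three stronger inferences are tempting but unsupported.

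- *The Per-Protocol violation list could alter the decision.* Section 9.2 does leave it late ("All efficacy evaluable subjects who have no major protocol violations, as defined by the Sponsor prior to database lock"), but Section 9.1 counts only Efficacy Evaluable subjects, and Section 9.3.3.2 uses the Per-Protocol set only for secondary efficacy analyses.
- *The weekly investigator calls reveal responses to the Sponsor.* Section 4.1 describes them as safety reviews.
- *The DMC's efficacy reports put response data in the Sponsor's hands.* Section 9.5 says "Efficacy data will also be provided to the DMC to allow assessment of benefit/risk for subjects". That committee is independent, and the section does not say the Sponsor receives those reports. The concern rests on the absence of masking and on investigator-read response.

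**Conclusion.** The point holds in a limited form. The plan permits the Stage 1 decision to be taken before the details that settle a borderline count are fixed. That lock follows the Stage 1 decision is an inference, but a sound one from Sections 9.1 and 10.1.5.

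The main effect is on the go/no-go: at a true rate of 11%, the probability of continuing rises from 0.319 to between 0.345 and 0.556 for q from 0.11 to 1, with q assumed throughout. The effect on type I error is smaller. With a cut of 12 it moves from 0.0494 to between 0.0502 and 0.0569, or as far as 0.0673 if the extra response also stays in the final total.

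A reader might infer that the stated 5% level is lost, or that the whole response analysis can be rewritten late. Neither follows. The 5% level is exceeded only under the Table 8 cut; under the rule in the text, type I error stays near 0.005. The main rules are already in the protocol. The unresolved choice between 12 and 15 is the most consequential item that a late SAP could settle with responses known: at a true rate of 23% it decides the conclusion in 23.4% of trials.

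**What to change.** - **Section 9.3:** replace the database-lock deadline with *finalized and signed before the Stage 1 data cut-off and before the Sponsor reviews any aggregate response data*.
- **Section 9.4:** state that this signed version governs both the Stage 1 and the final response-rate analyses, and that it fixes the data cut, Stage 1 membership, how unconfirmed responses and subjects with only 2 cycles count, and evaluability, including whether central Notch testing is done for everyone.
- **Later changes:** require a dated protocol amendment for any later change to these items.
- **Section 9.1:** reconcile the 15-or-more rule with Table 8 by the same date. Only a cut of 12 reproduces the stated power and type I error.

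The cost is that the SAP is written earlier. The SAP timing change alters no design figure and adds no patients or visits.

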9.5. Data Monitoring Committee (DMC)

An independent Data Monitoring Committee (DMC) will be assigned by the Sponsor prior to the beginning of the study. Throughout the study, the DMC will monitor safety parameters at regular intervals (approximately quarterly) after at least 3 subjects have been treated for at least 2 cycles (after the first on-treatment radiographic assessment) and then periodically as specified in the DMC charter. Efficacy data will also be provided to the DMC to allow assessment of benefit/risk for subjects. The DMC may recommend stopping the study if at any time during the study there are unacceptable AEs or safety concerns as described in the protocol stopping rules defined in the DMC charter.

For each DMC meeting, pre-specified reports will be provided. In addition, the DMC Chair will be provided with or have access to periodical safety and efficacy reports as specified in the DMC charter. The DMC Chair may share these reports with the DMC or convene additional meetings of the DMC at his/her discretion. The DMC Chair may request additional safety and efficacy data based on the review of study data.

Further details regarding data safety monitoring guidelines will be included in the DMC Charter, which is the governing document that supersedes this section of the protocol.

10. SUPPORTING DOCUMENTATION AND OPERATIONAL CONSIDERATIONS

10.1. Appendix 1: Regulatory, Ethical, and Study Oversight Considerations

10.1.1. Ethical Aspects

The Sponsor, contract research organization (CRO), and the Investigator must comply with all instructions, regulations, and agreements in this protocol and applicable ICH and GCP guidelines and conduct the study according to local regulations. The Investigator may delegate responsibilities for study-related tasks where appropriate to individuals sufficiently qualified by education, training, and experience, in accordance with applicable ICH and GCP guidelines. The Investigator should maintain a list of the appropriately qualified persons to whom significant study-related duties have been delegated. The Investigator is responsible for supervising those individuals and for implementing procedures to ensure the integrity of the tasks performed and any data generated.

10.1.1.1. Independent Ethics Committee (IEC)/Institutional Review Board (IRB) and Regulatory Authorities

Before initiation of the study at each study site, the protocol, the ICF, other written material given to the subjects, and any other relevant study documentation will be submitted to the appropriate IEC/IRB. Written approval of the study and all relevant study information must be obtained before the study center can be initiated or the investigational product is released to the Investigator. Any necessary extensions or renewals of IEC/IRB approval must be obtained for changes to the study such as amendments to the protocol, the ICF or other study documentation. The written approval of the EC/IRB together with the approved ICF must be filed in the study files.

It is the responsibility of the Sponsor to obtain and maintain independent approval from the applicable Regulatory Authorities to conduct the study in accordance with applicable regulatory requirements. It is the responsibility of the Sponsor to ensure that a positive opinion from the IEC/IRBs to conduct the study in accordance with applicable regulatory requirements is in place.

Relevant study documentation will be submitted to the regulatory authorities of the participating countries, according to local/national requirements, for review and approval before the beginning of the study. On completion of the study, the regulatory authorities will be notified that the study has ended.

10.1.1.2. Declaration of Helsinki/Good Clinical Practice

The Declaration of Helsinki is the accepted basis for clinical study ethics and must be fully followed and respected by all engaged in research on human beings. Any exceptions must be justified and stated in the protocol. The latest version of the Declaration of Helsinki is available under <http://www.wma.net/en/30publications/10policies/b3/index.html.pdf>. Additionally, the Investigator(s) and all parties involved in this study should conduct the study in adherence to the ethical principles based on the Declaration of Helsinki, ICH-GCP guidelines, and the applicable national and local laws and regulatory requirements.

10.1.1.3. Subject Information and Informed Consent

It is the responsibility of the Investigator to obtain written informed consent from each subject participating in this study, after adequate explanation of aim, importance, anticipated benefits, and potential hazards and consequences of the study according to applicable local laws. Written informed consent must be obtained before any study-specific procedures are performed. It must be also explained to the subject that he/she is completely free to refuse to enter the study or to withdraw from it at any time for any reason without incurring any penalty or withholding of treatment on the part of the Investigator.

With the declaration of consent the subject agrees that data on his/her medical history are recorded within the framework of the clinical study and that they are transferred to the Sponsor in a pseudo-anonymized manner. Subjects will be informed that their race and ethnicity will be collected and will be used during analysis of study results.

The subject also agrees to allow the monitor/auditor/health authorities to verify the collected subject data against the subject's original medical records for the purpose of source data verification.

The ICF – personally signed and dated by the subject and the Investigator – must be kept in the Investigator's study file by the Investigator(s) and documented in the eCRF and the subject's medical records. The Investigator confirms to the Sponsor to obtain the written informed consent from any subject before participating in the study.

If new information becomes available that may be relevant to the subject's willingness to continue participation in the study, a new ICF will be approved by the EC(s)/IRB(s) (and regulatory authorities, if required). If new safety information results in significant changes in the risk/benefit assessment, the consent form should be reviewed and updated if necessary. All subjects (including those already being treated) should be informed of the new information and must give their written informed consent to continue in the study.

If the family doctors are informed of their subjects' participation in the clinical study, this should be mentioned in the consent form.

10.1.1.4. Personal Data Protection

The study will be conducted in accordance with the data protection laws that apply in a particular country and jurisdiction.

The Sponsor complies with the principle of subject's right to protection against invasion of privacy. Throughout this study, all subject data will be identified only by a subject identification number. The personal data will be blinded in all data analyses. The subject must be informed and consent as required that authorized personnel of the Sponsor such as study monitor, auditor etc. and relevant health regulatory agency will have direct access to personal medical data to assure a high-quality standard of the study.

At the subject's request, medical information may be given to his or her personal physician or other appropriate medical personnel responsible for his or her welfare. Personal physician will be notified by site personnel of subject participation in the study.

Monitors, auditors, and other authorized agents of the Sponsor and/or its designee, the IEC(s)/IRB(s) approving this research, and the US FDA, as well as that of any other applicable agency(ies), will be granted direct access to the study subjects' original medical records for verification of clinical study procedures and/or data, without violating the confidentiality of the subjects to the extent permitted by the law and regulations. In any presentations of the results of this study or in publications, the subjects' identity will remain confidential.

All personal data collected and processed for the purposes of this study should be managed by the Investigator and his/her staff with adequate precautions to ensure confidentiality of those data, and in accordance with the Health Insurance Portability and Accountability Act [US Department of Health and Human Services. The Health Insurance Portability and Accountability Act (HIPAA) of 1996 (P.L.104-191) [HIPAA]. <http://aspe.hhs.gov/admnsimp/pl104191.htm>. Effective August 21, 1996.], applicable to national and/or local laws and regulations on personal data protection.

